9.6 Toxicity Management

The grading system for drug toxicities is located in the DAIDS Table for Grading the Severity of Adult and Pediatric Adverse Events, Version 1.0, December 2004 (Clarification August 2009), which can be found on the DAIDS RSC Web Site: <http://rsc.tech-res.com/safetyandpharmacovigilance/>. Participants experiencing side effects related to losartan, will be evaluated immediately by a study physician and may be referred to their primary HIV provider for evaluation and treatment if indicated. Subjects who develop drug-related toxicity of Grade 1 or 2 may continue study participation. If a participant experiences any drug-related toxicity >Grade 2 and it is judged to be due to losartan, losartan will be discontinued. If a participant experiences any drug-related toxicity >Grade 2 and it is judged to be due to Gardasil, further doses of Gardasil will not be administered.

All subjects who experience AEs will continue to be followed until resolution or stabilization of the issue.

9.7 Halting and Stopping Rules

9.7.1 Halting Rules for the Protocol

At the initial meeting, which will take place during the administrative start-up period of this project and prior to the enrollment of any subjects, the DSMB will develop the DSMB charter, which includes triggers set for stopping the study for safety concerns and for efficacy. Subsequent review of serious, unexpected and related adverse events by the Medical Monitor, DSMB, ethics review committee or IRB, the sponsor(s), and other regulatory authorities may also result in suspension of further trial interventions/administration of study agent at a site. The study sponsor(s) and other regulatory agencies retain the authority to suspend additional enrollment and study agent(s)/intervention(s) administration for the entire study as applicable.

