2.4 Potential Risks and Benefits

2.4.1 Potential Risks

Potential risks of study procedures (venipuncture, inguinal LN biopsy, and colonoscopy with GALT biopsies) are detailed in Section 7.1 and in consent forms. According to the Losartan package insert, the most severe risks of losartan use include teratogenicity in the setting of pregnancy, hypersensitivity, symptomatic hypotension, worsening of renal function, and electrolyte abnormalities. The most common side effects of losartan include fatigue, weakness, diarrhea, chest pain, tachycardia and anemia.

Subjects will be rigorously screened to ensure that they are at low risk for complications due to losartan and they will be monitored closely for side effects and signs of toxicity. The most common side effects of Gardasil include headache, fever, nausea, dizziness and injection site reactions. Severe reactions, including hypersensitivity, are rare. The most common side effects of Stribild are new onset or worsening of renal impairment, bone effects, fat distribution and immune reconstitution syndrome. The most common side effects of Stribild include nausea, diarrhea, abnormal dreams, headache, rash, fatigue, dizziness, insomnia, flatulence, somnolence, ocular icterus and jaundice. The most common side effects of Prezista are drug –induced hepatitis, skin reactions ranging from mild to severe, use with caution with a known sulfonamide allergy, new onset diabetes or hyperglycemia, redistribution/accumulation of body fat or immune reconstitution syndrome and subjects with hemophilia may develop increased bleeding events, The most common side effects of Prezista include diarrhea, nausea, rash, headache, abdominal pain and vomiting.

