4. STUDY DESIGN

4.1 Description of the Study Design:

This is a randomized, double-blind, placebo-controlled trial of 50 HIV-1 infected individuals on stable ART randomized in a 1:1 ratio to losartan (50 mg orally daily titrated to 100 mg daily) vs placebo for 30 months. We plan to enroll a total of 63 HIV infected subjects to ensure that 50 complete the protocol. All HIV infected subjects will undergo biopsies of inguinal lymph node (LN) and gut associated lymphatic tissue (GALT) for primary endpoint analysis at baseline, 12 and 30 months after study enrollment. Blood will be collected at least quarterly throughout the study and an intensive blood pharmacokinetic (PK) study will be conducted at month 1. All HIV infected subjects will be vaccinated with the quadrivalent human papillomavirus (HPV) vaccine at months 23, 25 and 29.5. 5 HIV uninfected control subjects will also be enrolled. They will not receive study agents or HPV vaccination and will undergo blood draw and inguinal LN biopsy at one time point only. We anticipate completing subject enrollment over a 14 month period and plan to complete all subject follow up 44 months after the first subject is enrolled.

4.2 Study Endpoints:

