9.1.3 Definition of a Suspected Unexpected Serious Adverse Reaction (SUSAR)

An AE that is:

- Serious (i.e., an SAE),
- Related (i.e., there is a reasonable possibility that the AE may be related to the study product), and
- Unexpected (i.e., an AE whose nature or severity [intensity] is not consistent with the applicable product information found in an investigator's brochure, a package insert or a summary of agent characteristics).

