9.4 Reporting Procedures

9.4.1 AEs to be Reported

The following AEs will be promptly reported within three reporting days to the DSMB and the DAIDS medical monitor:

- all cancers, all autoimmune diseases, all fetal losses associated with an AE,
- all overdoses associated with an AE, and
- any definitely related, unexpected, and serious adverse events (SUSARS).

Other AEs or unanticipated problems will be reported to the IRB and DSMB within their reporting timelines (such as annual review or if prompt reporting is required, within the urgent reporting timeline requirements).

At the time of the initial report, the following information should be provided:

- Study identifier,
- Subject number,
- A description of the event,
- Date of onset,
- Current status,
- Whether study treatment was discontinued,
- The reason why the event is classified as serious, and
- Investigator assessment of the association between the event and study treatment.

Copies of each report and documentation of applicable IRB notification and receipt will be kept in the Clinical Investigator's binder. All reportable AEs will be followed until satisfactory resolution or until the PI or Sub-investigator deems the event to be chronic or the participant to be stable. If a previous SAE that was not initially deemed reportable under expedited reporting criteria is later found to fit the criteria

for reporting, the PI will submit the SAE in a written report as soon as possible. The full list of adverse events and complications will be reviewed by the IRB and DSMB on an annual basis.

Table: Expedited Reporting to IRB, DSMB and DAIDS

Expedited Reporting to Whom	Criteria for Reporting	Timeframe	Submission Format
IRB	Unanticipated death of a locally enrolled subject(s); New or increased risk; Any adverse event that requires a change to the protocol or consent form; Unanticipated problems; Refer to the IRB website for complete details on required reporting criteria.	5 working days	Local IRB's standard reporting form
DSMB	1) SUSARS 2) all cancers, all autoimmune diseases, all fetal losses associated with an AE, and all overdoses associated with an AE 3) Unanticipated death of locally enrolled subject(s)	3 reporting days (defined as M-F, including holidays)	Submit AE/SAE CRF, and IRB Report form, if available.

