DAIDS	1) SUSARS 2) all cancers, all autoimmune diseases, all fetal losses associated with an AE, and all overdoses associated with an AE 3) Grade 3 and 4 AEs that are attributed to study procedures (graded as per section 9.3.1 above)	3 reporting days (defined as M-F, including holidays)	Submit SAE/AE CRF to DAIDS medical officer.

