The DSMB will then meet at least once annually to examine the accumulated safety and enrollment data, review study progress, and discuss other factors (internal or external to the study) that might impact continuation of the study as designed. The frequency of meetings may be increased if unanticipated adverse events (AEs) or safety issues are observed or enrollment rate exceeds expectations. A DSMB meeting may be requested by DSMB members, study sponsor, industrial collaborator, IRB, or study PI at any time to discuss safety concerns. Decisions to hold ad hoc meetings will be made by the DSMB Chair. Meetings may be held by conference calls or videoconferences or as face-to-face meetings. In the event a DSMB member cannot attend a meeting, he/she may receive a copy of the closed session DSMB report and either participate by conference call or provide written comments to the DSMB Chair for consideration at the meeting.

DSMB meetings will be held in two parts. First, an open section will be held in which demographic data and trial progress will be discussed. Quality assurance and compliance issues may be discussed in this

session, and this session is open to investigators, sponsors, funder, patient advocates, and others as appropriate. Open sessions will be followed by closed sections in which only the DSMB members and specifically invited guests will attend. In closed sessions, the outcomes data will be assessed and recommendations formulated. Closed session meetings may be conducted by teleconference at the discretion of the DSMB Chair.

Meeting notes will be prepared from both the open and closed sessions within 2 weeks of the meetings. The DSMB will not share confidential information, particularly trial interim data with anyone, including the PI. The recommendations of the DSMB will be communicated in writing to the Trial Sponsor, PI, IRB, and/or appropriate regulatory agency. The recommendations open to the DSMB will include the following:

- No action required; continue trial as planned.
- Early termination due to a clear benefit or harm in the interventional group.
- Early termination due to futility.
- Termination of recruitment and/or treatment within a subgroup or single arm of a multi-arm trial.
- Extending recruitment or follow up for all or individual arms of the protocol.

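### No expedited DSMB or DAIDS report is pre-specified for Grade 3-4 losartan-related toxicity that fits the package insert; the only scheduled DSMB review is annual, when about 45-54 of 63 participants could be enrolled

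*Combined protocol and SAP*

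**What the plan says.** **Suspension (9.7.1).** Before enrolment the DSMB writes a charter with triggers for safety and efficacy. The protocol then adds a further possible route to suspension: "Subsequent review of serious, unexpected and related adverse events by the Medical Monitor, DSMB, ethics review committee or IRB". It gives no event type, grade or count for the charter triggers. Section 10.1.1 says the stopping guidelines rest on plans in the protocol.

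**Unexpected (9.1.3).** An unexpected event is "an AE whose nature or severity [intensity] is not consistent with the applicable product information found in an investigator's brochure, a package insert" or similar reference document.

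**Labelled risks (2.4.1).** Citing the losartan insert, the protocol says "the most severe risks of losartan use include teratogenicity in the setting of pregnancy, hypersensitivity, symptomatic hypotension, worsening of renal function, and electrolyte abnormalities".

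**Prompt reports (9.4.1 and its table; 9.4.2).** The DSMB hears within three reporting days of SUSARs, cancers, autoimmune diseases, fetal losses and overdoses with an AE, and unanticipated deaths. DAIDS receives the first five of these and also "Grade 3 and 4 AEs that are attributed to study procedures". Other AEs go to the IRB and DSMB on those bodies' own timelines, which may be annual, or urgent where prompt reporting is required.

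**Scheduled review.** Section 9.4.1: "The full list of adverse events and complications will be reviewed by the IRB and DSMB on an annual basis". Section 10.1.1: "The DSMB will then meet at least once annually to examine the accumulated safety and enrollment data".

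**The individual participant (9.6).** "If a participant experiences any drug-related toxicity >Grade 2 and it is judged to be due to losartan, losartan will be discontinued". Section 9.7.2 also removes that participant from the study.

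**The concern.** Losartan is a blood-pressure drug given here to people selected for HIV, alongside ART regimens whose interactions with it the protocol (2.2) says have not been studied extensively. The most foreseeable harm is more of the known, labelled toxicity than expected. The protocol anticipates this: its dose-escalation checks in 8.1.3 are systolic pressure, potassium and eGFR. Yet this class of event has no line of its own in the prompt-report lists.

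The table is also uneven. A Grade 3 event caused by a biopsy reaches DAIDS in three reporting days. A Grade 3 event caused by the study drug does not, unless it is a SUSAR or falls in another listed category, although 9.6 treats it as grave enough to stop losartan.

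At stake is whether a committee independent of the investigators sees an early cluster of such events while most participants are starting treatment, or learns of it at a yearly meeting. A charter trigger based on a count can operate between meetings only if the events reach the committee between meetings.

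**Working it through.** **1. Follow one event through the text.** Take a Grade 3 potassium or renal abnormality judged related to study drug, of a nature and severity that fits the insert.

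| Provision | Result |
|---|---|
| 9.1.3 | Consistent with product information, so not unexpected and not a SUSAR |
| 9.4.1 list; table, DSMB row | Not a SUSAR, cancer, autoimmune disease, fetal loss, overdose or unanticipated death: no three-day report |
| Table, DAIDS row; 9.4.2 | Grade 3-4 item covers study procedures only: no expedited report |
| 9.4.1, other AEs | DSMB timeline: annual, or urgent under a condition that is not defined |
| 9.6, 9.7.2 | Participant-level consequence only |

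A labelled event whose severity exceeds the label would be unexpected and, if serious and related, a SUSAR. The gap concerns events within the label.

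**2. The plan's enrolment figure.** Section 4.1 plans to "enroll a total of 63 HIV infected subjects to ensure that 50 complete the protocol", and 2.2 gives dropout of 20-25%. 50 / (1 - 0.20) = 62.5, rounded up to 63, which reproduces the figure at the lower end of the range. At 25%, 50 / 0.75 = 66.7, rounded up to 67.

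**3. Enrolment at the first annual review.** Inputs: 63 participants, 14 months of accrual (4.1), 1:1 allocation, and a DSMB meeting at least every 12 months (10.1.1). The initial meeting falls in the first two study months, before enrolment. Uniform accrual is my assumption. The start of the annual clock is not stated, so I vary it:

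- Clock starts at first enrolment: 63 x 12/14 = 54 enrolled (86%), about 27 on losartan.
- Clock starts 1 month earlier: 63 x 11/14 = 49.5.
- Clock starts 2 months earlier: 63 x 10/14 = 45 enrolled (71%), about 22 on losartan.

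**4. How many events that could mean.** The documents give no toxicity rate, so the rates p below are assumptions. The number of losartan participants with a related event above Grade 2 is taken as Binomial(n, p):

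| Assumed p | Expected, n = 22 | P(3 or more), n = 22 | Expected, n = 27 | P(3 or more), n = 27 |
|---|---|---|---|---|
| 5% | 1.1 | 0.095 | 1.35 | 0.150 |
| 10% | 2.2 | 0.380 | 2.7 | 0.515 |
| 20% | 4.4 | 0.846 | 5.4 | 0.928 |

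This counts everyone as having passed the risk period, including those just randomized, so it leans high. The exclusions in 5.2 for systolic pressure below 110, potassium above 5.0 and eGFR below 30 favour the lower rates.

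**The case against.** A reader might infer that event-driven review counts only unexpected related SAEs, and that labelled toxicity can reach the DSMB only once a year. The documents do not support that.

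- Section 9.2 requires the PI to assess every AE as a possible unanticipated problem. The criteria include unexpected frequency, and a positive finding goes promptly to the IRB and DSMB. An excess of known toxicity could qualify. The table also gives the IRB new or increased risk within five working days.
- Section 9.4.1 allows an urgent timeline for other AEs.
- In 9.7.1 the review of unexpected events is additional to the charter's safety triggers, which are not limited to unexpected events. The sponsor and regulators can also suspend without that limit.
- Section 10.1.1 sets annual meetings as a minimum, allows more for safety issues, and lets the PI, sponsor, IRB or members request one at any time.
- Section 9.3 has side effects reported to the PI or physician co-investigators daily and toxicity laboratory results reviewed in real time.
- Whether a given Grade 3-4 event fits the insert cannot be settled here, because 2.4.1 names risks without grades or frequencies.

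All of this stands, and it rules out any claim that such events cannot reach the DSMB early. It softens the gap without closing it. The 9.2 route asks a PI blinded to treatment (9.8) to judge, event by event and with no reference count, that a labelled toxicity has become too frequent. The condition for urgent reporting is undefined and ad hoc meetings are discretionary. The charter's content is not in these documents, and the protocol plans it is to draw on name no toxicity type, grade or count.

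**Conclusion.** The point holds as a gap in pre-specified reporting. No provision requires a prompt report to the DSMB or DAIDS of Grade 3-4 losartan-related toxicity that fits the package insert, although procedure-related events of the same grade are expedited to DAIDS. The only scheduled DSMB review is at least annual. By then about 45-54 of 63 participants (71-86%), some 22-27 of them on losartan, could be enrolled.

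That range rests on uniform accrual, a first review no sooner than the annual minimum, and a clock starting between two months before first enrolment and first enrolment itself. The event counts only illustrate assumed rates.

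Two related inconsistencies need reconciling. Section 9.4.1 limits its prompt SUSAR item to definitely related events, whereas 9.1.3 requires only a reasonable possibility. Section 8.1.3 allows re-challenge after a related event of Grade 3 or higher, whereas 9.6 discontinues losartan and 9.7.2 removes the participant. This review takes no position on which clinical rule is right.

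**What to change.** Add one line to the 9.4.1 list, to the DSMB and DAIDS rows of its table, and to 9.4.2: any AE above Grade 2 judged related to study drug (losartan/placebo), whether or not expected, is reported within the same three reporting days. This reuses the grade in 9.6 and 9.7.2 and the existing reporting clock, and the losartan/placebo wording keeps it workable under the blind. Any trigger the existing DSMB sets in its charter could then operate between meetings.

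The suspension wording in 9.7.1 and the individual dosing and stopping rules need not change for this. Separately, align the relatedness wording of 9.4.1 with 9.1.3, and have the investigators reconcile 8.1.3 with 9.6 and 9.7.2.

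The cost is a protocol wording change, a few more AE forms to recipients already in place, and possibly an ad hoc meeting. No visit, committee or participant is added.

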9.7.2 Stopping Rules for an Individual Participant

Subjects may withdraw from the study (and all follow-up procedures) for any reason and at any time. Participants may also choose to discontinue study medication and continue all follow-up procedures. This is most likely in the event of a toxicity that, in the opinion of the investigators, is related to the study agents.

If a subject withdraws, attempts will be made to schedule and conduct an early termination visit as described in section 8.1.11. The reason and date of withdrawal will be documented on the subject's CRF. Date of withdrawal will be documented as the date of last study drug treatment, not the date that the decision to withdraw was made. Participants will be followed after withdrawal from the study for 3 months after discontinuation. All AEs during that period will be reported.

The PIs may withdraw participants to protect their safety or if participants are unable or unwilling to comply with visits, study procedures, or study medication. Participants will be removed from the study if they experience any drug-associated toxicity > grade 2 and it is judged to be due to losartan (e.g., a complication of the biopsy procedure may not necessitate removal from the study). Subjects will not be withdrawn if they experience toxicity > grade 2 that is deemed due to Gardasil but will not continue to be given Gardasil. Subjects will also be removed in the event of pregnancy. Healthy controls will be removed from the study if they experience rash, moderate GI symptoms and/or symptoms consistent with clinical hepatitis with no other medically reasonable cause. Other exit criteria include:

- completion of the study,
- withdrawal of consent,
- moving to an area that would prohibit the subject from returning for visits, and
- death.

Even though subjects may be withdrawn prematurely from the study, we will continue to collect survival data on such subjects throughout duration of the 30 months. If a subject withdraws consent to participate in the study, attempts will be made to obtain permission to record survival data up to the 30-month end point. Methods used for follow up will include at least 5 phone calls and 3 letters to the participant.

Any subject withdrawn from the study prior to Month 1 will be replaced by another enrolled participant to meet study objectives.

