Dose Reduction: Tolerability, side effects, and clinical laboratory monitoring will be assessed at each study visit (via participant report and clinical labs), and at any other time point at the discretion of the clinical site investigator. Adverse events that are assessed as related to study drug will prompt re-evaluation via phone or as an adverse event visit, per clinical discretion of the site investigator. If this event worsens or does not resolve after re-evaluation, then study medication dose should be decreased (i.e., from 100mg to 50mg) or stopped (if taking 50mg daily). If signs and symptoms resolve after 2 weeks, then the participant may resume or increase dose (i.e., back to 100mg if previously reduced to 50mg daily), per the clinical discretion of the site investigator.

Stopping Study Medication: If an adverse event of grade ≥ 3 is assessed as related to study drug, study medication should be stopped and the participant should be re-evaluated in 2 weeks. If a grade 2 rash is persistent, study medication may also be stopped at the discretion of the site investigator and the participant should be re-evaluated in 2 weeks. If signs and symptoms resolve after 2 weeks, then the participant may be re-challenged at a lower dose (i.e., at 50mg if previously taking 100mg daily) per the clinical discretion of the site investigator. If study medication is stopped for an adverse event that is later determined NOT to be related to study medication, then the medication may be resumed at 50mg and increased to 100mg per initial criteria for dose escalation and at the discretion of the clinical site investigator.

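### Section 9.7.2 removes participants for losartan toxicity above grade 2, is inconsistent with 8.1.3 and 9.6, and leaves no provision for endpoint tissue or blood afterwards

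*Combined protocol and SAP*

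**What the plan says.** Three sections deal with a related event of grade 3 or above, which is the same set of grades as above grade 2.

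- **8.1.3 (Stopping Study Medication).** An event of this grade that "is assessed as related to study drug, study medication should be stopped and the participant should be re-evaluated in 2 weeks". If it has resolved by then, "then the participant may be re-challenged at a lower dose", at the site investigator's discretion.
- **9.6.** "Subjects who develop drug-related toxicity of Grade 1 or 2 may continue study participation". For toxicity above grade 2, when the event occurs "and it is judged to be due to losartan, losartan will be discontinued". Removal from the study is not mentioned.
- **9.7.2.** "Participants will be removed from the study if they experience any drug-associated toxicity > grade 2", again on condition that the toxicity is judged due to losartan.

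Section 9.7.2 contains two other relevant rules. One is an option: "Participants may also choose to discontinue study medication and continue all follow-up procedures". The next sentence adds: "This is most likely in the event of a toxicity that, in the opinion of the investigators, is related to the study agents". The other concerns Gardasil: toxicity above grade 2 attributed to the vaccine ends vaccination but does not end participation.

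After a participant leaves, the protocol provides for an early termination visit (8.1.11: medical assessment and return of drug), three months of adverse event follow-up, following of adverse events until they resolve or stabilize, and survival status to month 30. Table 1 in section 8.2 has no early termination column.

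**The concern.** The primary endpoint is lymphoid tissue fibrosis, measured on biopsies at baseline, month 12 and month 30. If removal ends those biopsies, primary-endpoint data are lost because of an event attributed to losartan. Attribution is blinded, so some placebo participants could also be removed. True losartan reactions arise only in the losartan arm, however, so more removals there are plausible.

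The mixed model in sections 11.1 and 11.5 can use month-12 tissue from someone removed later. It has no post-baseline tissue from anyone removed before month 12, and in effect treats such participants as if they had followed others in their arm. Enrolling 63 to obtain 50 completers restores the head count but not these participants' tissue. Section 9.7.2 also replaces anyone withdrawn before month 1, a period that includes the day-14 dose increase.

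There is a practical problem too. Staff managing a grade 3 event find three different instructions and need one.

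**Working it through.** **1. The rules side by side, for a grade 3 or higher event**

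| Section | Trigger | Study drug | Study participation |
|---|---|---|---|
| 8.1.3 | Assessed as related to study drug | Stop; re-evaluate at 2 weeks; discretionary lower-dose re-challenge | Not addressed; re-challenge implies staying in |
| 9.6 | Judged due to losartan | Discontinue | Not addressed above grade 2 |
| 9.7.2 | Judged due to losartan | Not addressed separately | Removed |

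For an event judged due to losartan, an investigator satisfies all three sections only by not using the re-challenge permission.

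**2. What removal means for data.** No sentence says that biopsies stop on removal; this is an inference. The main support is that the listed post-withdrawal data contain no biopsy and no research blood, and that the neighbouring Gardasil rule is worded as the contrasting case in which the participant stays. The stop-drug-and-continue option is a participant's choice. The removal sentence is mandatory and makes no exception for it.

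**3. Loss per removed participant (from Table 1)**

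- Biopsy time points: baseline, 12 and 30 months = 3.
- Post-baseline serum and plasma/PBMC collections: month 1 (1) + months 3, 6, 9, 15, 18, 21, 27 (7) + months 12, 23, 25, 29.5, 30 (5) = 13.
- Removed just after month 1: biopsies lost 2 of 3; collections lost 13 − 1 = 12 of 13.
- Removed just after month 12: biopsies lost 1 of 3; collections obtained are months 1, 3, 6, 9, 12 = 5, so 13 − 5 = 8 of 13 lost.

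These counts apply to any withdrawal at those times. They measure the loss per person, not how often it happens.

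**4. Is this mainly a loss of power?** Section 11.2 gives power 0.86 for a difference of 0.7, SD 0.81 (log scale), 25 per group. With two-sided 0.05 assumed (section 11.5 gives no number), power ≈ Φ(δ / (σ√(1/n₁ + 1/n₂)) − 1.96).

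- 25 and 25: 0.7 / (0.81 × √0.08) = 3.055; Φ(1.095) = 0.863, which reproduces the plan.
- 20 and 25 (assumed loss of 5 in the losartan arm): 0.7 / (0.81 × √0.09) = 2.881; Φ(0.921) = 0.821.
- Assumed losses of 1 and 3 give 0.856 and 0.840.

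The losses of 1 to 5 are illustrative. Even at 5 the fall in power is modest. The issue is which participants are missing, not how many.

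**5. Size of bias.** This would need the rate of losartan-related events above grade 2 in each arm, and how collagen changes in those removed. The documents give neither, so no figure is computed.

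**The case against.** A reader might infer that the sections contradict each other outright and that the re-challenge permission can never be used. The documents do not support that.

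- The triggers are worded differently. Section 8.1.3 speaks of an event assessed as related; 9.7.2 of toxicity judged due to losartan. The causality scale in 9.3.2 includes a possibly related category in which other factors may have contributed. A blinded investigator could place an event there and re-challenge without judging it due to losartan. The protocol does not define the stricter phrase, so this reading is arguable.
- The re-challenge sentence also follows the provision for persistent grade 2 rash, which 9.7.2 does not reach.
- Re-challenge is optional, so no two mandatory duties collide.

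A reader might also take it as stated that endpoint collection ends on removal. It is not stated. The sentence "Subjects may withdraw from the study (and all follow-up procedures) for any reason and at any time" describes voluntary withdrawal and does not define removal by the investigator. Section 9.6 names only drug discontinuation above grade 2. The stop-drug-and-continue option shows that the design contemplates keeping people after toxicity.

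Finally, few such events may occur. Section 2.2 cites good tolerability of this dosing in non-hypertensive patients; section 5.2 excludes low blood pressure, raised potassium, poor renal function and prior intolerance; and the dose increase at day 14 is conditional. Ending participation after a serious drug reaction is also a defensible caution when the remaining procedures are node excision and sedated colonoscopy with no direct benefit.

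All of this narrows the point. What survives is that, for events judged due to losartan, removal is mandatory as written, and nothing in the text provides for tissue or research blood afterwards.

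**Conclusion.** The point holds in limited form. Sections 8.1.3, 9.6 and 9.7.2 are inconsistent for events above grade 2 judged due to losartan. Followed as written, 9.7.2 leaves a removed participant without provision for the remaining biopsies: 2 of 3 time points if removed between baseline and month 12, 1 of 3 if between months 12 and 30.

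This rests on two assumptions: that removal ends scheduled procedures, which is inferred from what the protocol provides afterwards, and that removals for this reason would be more frequent on losartan, which is plausible but not shown.

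A reader might go further and conclude that the primary comparison is biased. The documents do not support that: they give no event rate, and the planned non-completion (63 − 50 = 13 of 63, or 20.6%) is an all-cause figure with no share assigned to drug toxicity. The size of any bias is unknown and may be small. The change is worth making because it is cheap, not because harm to the result has been demonstrated.

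**What to change.** 1. Align 8.1.3, 9.6 and 9.7.2 on one study-drug rule for losartan-related events above grade 2, either permanent stop or discretionary re-challenge, decided on clinical grounds. Use one causality phrase throughout, tied to the scale in 9.3.2.
2. In 9.7.2, replace removal from the study with text such as: study drug is stopped or handled under that rule; scheduled blood draws and the month-12 and month-30 biopsies continue unless consent is withdrawn or the procedure is medically unsuitable; these participants are analysed in their randomized arm.

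This follows the model that 9.7.2 already uses for Gardasil and for voluntary discontinuation of study medication, and adds no procedure beyond those scheduled.

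Cost: a protocol amendment with IRB approval and DAIDS registration (section 13.1), and a check that the consent form covers biopsies after study drug is stopped. Participants off drug will dilute the estimated effect somewhat. Some will decline, or be unsuitable for, a further node excision and colonoscopy, so the missing data will be reduced rather than eliminated.
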